## 8 DATA AND SAFETY MONITORING PLAN (DSMP)

### Data and Safety Management Overview

The Medical College of Wisconsin (MCW) Data and Safety Monitoring Committee (DSMC) and the MCW Institutional Review Board (IRB) will approve protocol-specific DSM plans. A local, investigator-initiated trial will be required to be continuously monitored by the principal investigator of the study with safety and progress reports submitted to the DSMC.

The DSMP for this study will involve the following entities:

#### 8.1 Study Team

The study team minimally consists of the principal investigator, the clinical research coordinator, regulatory specialist and the study biostatistician. While subjects are on study, the principal investigator will meet regularly with the research coordinator and the study biostatistician to review study status. This review will include but not be limited to reportable SAEs and UPIRSOs and an update of the ongoing study summary that describes study progress in terms of the study schema. The appropriateness of further subject enrollment and the specific intervention for a next subject enrollment is addressed. All meetings, including attendance, are documented.

#### 8.2 Quality Assurance

This protocol was classified as high risk and will be reviewed internally by the MCW Cancer Center Clinical Trials Office Quality Assurance Staff according to the MCWCC Data and Safety Monitoring Plan and current version SOP, 6.5.2 Internal Quality Assurance Reviews.

#### 8.3 Clinical Trials Office

The MCWCC Clinical Trials Office [CTO] provides administrative assistance and support to the DSMC.

#### 8.4 DSMC

The Medical College of Wisconsin Cancer Center places the highest priority on ensuring the safety of patients participating in clinical trials. Every cancer interventional trial conducted at MCW includes a plan for safety and data monitoring.

More information can be found related to the MCWCC Data and Safety Monitoring Plan at the MCWCC website ([Data and Safety Monitoring Plan](#)).

This study will be reviewed by the Medical College of Wisconsin Cancer Center Data and Safety Monitoring Committee (MCWCC DSMC). A summary of the MCWCC DSMC activities are as follows:

- Review the clinical trial for data integrity and safety.
- Review all DSM reports.
- Submit a summary of any recommendations related to study conduct.
- Terminate the study if deemed unsafe for patients.

A copy of the MCWCC Data and Safety Monitoring Plan and membership roster will be maintained in the study research file and updated as membership changes. The committee will review reports

from the study PI twice annually (review frequency may change based on study risk per DSMC discretion) and provide recommendations on trial continuation, suspension or termination, as necessary.

Any available DSMC letters will be submitted to the IRB of record as required.

## **9 REGULATORY COMPLIANCE, ETHICS AND STUDY MANAGEMENT**

### **9.1 Ethical Standard**

This study will be conducted in accordance with the ethical principles that have their origin in the Declaration of Helsinki as stated in 21 CFR §312.120(c)(4); consistent with GCP and all applicable regulatory requirements.

### **9.2 Regulatory Compliance**

This study will be conducted in compliance with:

- The protocol
- Federal regulations, as applicable, including: 21 CFR 50 (Protection of Human Subjects/Informed Consent); 21 CFR 56 (Institutional Review Boards) and §312 (Investigational New Drug Application; and 45 CFR 46 Subparts A (Common Rule), B (Pregnant Women, Human Fetuses and Neonates), C (Prisoners), and D (Children), GCP/ICH guidelines, and all applicable regulatory requirements. The IRB must comply with the regulations in 21 CFR §56 and applicable regulatory requirements.

### **9.3 Prestudy Documentation**

Prior to implementing this protocol at MCWCC, the protocol, informed consent form and any other information pertaining to participants must be approved by the MCW IRB.

### **9.4 Institutional Review Board**

The protocol, the proposed informed consent form and all forms of participant information related to the study (e.g., advertisements used to recruit participants) will be reviewed and approved by the MCW Institutional Review Board. Prior to obtaining MCW approval, the protocol must be approved by the Medical College of Wisconsin Cancer Center Scientific Review Committee. The initial protocol and all protocol amendments must be approved by the IRB prior to implementation.

### **Informed Consent Process**

Informed consent is a process that is initiated prior to the individual's agreeing to participate in the study and continues throughout the individual's study participation. Extensive discussion of risks and possible benefits of this therapy will be provided to the subjects and their families. Consent forms describing in detail the study interventions/products, study procedures and risks are given to the subject and written documentation of informed consent is required prior to starting intervention/administering study product.

Potential subjects will be told, and a statement will be included that this study is designed to determine both safety and effectiveness. The consent forms will include the approved MCW IRB template language.

Consent forms will be IRB approved and the subject (and legally authorized representative, if necessary) will be asked to read and review the document. The treating physician or the investigator will explain the research study to the subject and answer any questions that may arise. The study coordinator may complete the consenting process. In accordance with 46 CR 46.111, the subject will sign and date the informed consent document prior to any procedures being done specifically for the study.

A witness should only sign when required, per FH/MCW IRB policy. If a witness signs the document when not required, the study staff should document in the legal medical record (or note to file) the relationship to the patient and why a witness signed. (i.e., "Although not required, the subject's spouse was present during the consenting process and signed as the witness." Or "Although not required, hospital staff was present for consenting process and signed as a witness.")

The subjects will have the opportunity to discuss the study with their surrogates or think about it prior to agreeing to participate. The subjects may withdraw consent at any time throughout the course of the trial.

A copy of the informed consent document will be given to the subjects for their records. The rights and welfare of the subjects will be protected by emphasizing to them that the quality of their medical care will not be adversely affected if they decline to participate in this study. If there are changes to the consent form, all revisions will be reviewed with study subject at the next appropriate opportunity. Patients who require reconsenting will be defined in the IRB-approved amendment submission. The process for obtaining informed consent will again be performed. Study subjects will not be reconsented for continuing reviews. The MCWCC CTO will follow the MCW/FH IRB's policy for subjects who demonstrate limited English proficiency or limited literacy.

After the subject's visit in which the consent is signed, it is documented in the clinic chart that the consent has been signed and that all questions have been answered to the subject's satisfaction after adequate time for review of the consent. It is also documented that a copy of the consent was given to the subject. The original consent is kept with the subject's study file, and a copy of the consent is sent to the OCRIICC office, which will then submit to HIM a copy of the signed consent to be scanned into EPIC, the legal medical record.

## **9.5 Subject Confidentiality and Access to Source Documents/Data**

Subject confidentiality is strictly held in trust by the sponsor-investigator, participating investigators, and any staff, and the sponsor. This confidentiality includes the clinical information relating to participating subjects, as well as any genetic or biological testing.

The study protocol, documentation, data and all other information generated will be held in strict confidence. No information concerning the study, or the data will be released to any unauthorized third party without prior written approval of the principal investigator.

The conditions for maintaining confidentiality of the subjects' records are required for the life of the data. These rules apply equally to any and all MCWCC projects.

One risk of taking part in a research study is that more people will handle the personal health information collected for this study. The study team will make every effort to protect the information and keep it confidential, but it is possible that an unauthorized person might see it. Depending on the kind of information being collected, it might be used in a way that could embarrass the subject or affect his/her ability to get insurance.

While data are being collected and after all data have been collected but are still in the process of being analyzed, the subject's data/PHI are stored in the locked clinical research office in the Clinical Trials Office. Databases in which the study subject information is stored and accessed are password protected, allowing for limited access by authorized personnel only. Data/PHI kept in the case report forms contain the study identifiers, subject initials, date of birth and date of service.

Personal identifiers, such as name and medical record number, will be removed from accompanying lab reports and test results. Any data/PHI that are not stored for the purposes of the study are shredded in the Clinical Trials Office.

After all study queries and analyses are completed, the data/PHI will not be destroyed but will be archived in a secure long-term storage site in order to keep an accurate record of screened and enrolled subjects for the sponsor and potential audit purposes only specific for this study.

## **9.6 Protection of Human Subjects**

### **9.6.1 Protection from Unnecessary Harm**

Each clinical site is responsible for protecting all subjects involved in human experimentation. This is accomplished through the IRB mechanism and the informed consent process. The IRB reviews all proposed studies involving human experimentation and ensures that the subject's rights and welfare are protected and that the potential benefits and/or the importance of the knowledge to be gained outweigh the risks to the individual. The IRB also reviews the informed consent document associated with each study in order to ensure that the consent document accurately and clearly communicates the nature of the research to be done and its associated risks and benefits.

### **9.6.2 Protection of Privacy**

As noted, patients will be informed of the extent to which their confidential health information generated from this study may be used for research purposes. Following this discussion, they will be asked to sign informed consent documents. The original signed document will become part of the patient's medical records, and each patient will receive a copy of the signed document.

## **9.7 Changes in the Protocol**

Once the protocol has been approved by the MCW IRB, any changes to the protocol must be documented in the form of an amendment. The amendment must be signed by the investigator and approved by IRB prior to implementation.

If it becomes necessary to alter the protocol to eliminate an immediate hazard to patients, an amendment may be implemented prior to IRB approval. In this circumstance, however, the investigator must then notify the IRB in writing within five working days after implementation.

The IRB may provide, if applicable regulatory authority(ies) permit, expedited review and approval/favorable opinion for minor change(s) in ongoing studies that have the approval /favorable opinion of the IRB. The investigator will submit all protocol modifications to the sponsor and the regulatory authority(ies) in accordance with the governing regulations.

Changes to the protocol may require approval from the sponsor.

Any departures from the protocol must be fully documented in the source documents.

## **9.8 Investigator Compliance**

The investigator will conduct the study in compliance with the protocol given approval/favorable opinion by the IRB and the appropriate regulatory authority(ies).

# **10 DATA HANDLING AND RECORD KEEPING**

## **10.1 Overview**

Every effort is made to uphold the integrity of the project, the research, the institution, and the researchers involved. Data collection guidelines and methodologies are carefully developed before the research begins. Investigators focus on the following to ensure data integrity: well-trained data collectors/recorders to ensure consistency and quality, well-designed data collection protocols and ongoing monitoring. In this way, study rigor and validity are maintained. Data is protected from physical damage as well as from tampering, loss or theft. This project's data management is a multidisciplinary activity that includes investigators, research coordinators and nurses, data managers, support personnel, biostatisticians and database programmers. Quality control will be applied to each stage of data handling to ensure that all data are reliable and have been processed correctly.

## **10.2 Data Management Responsibilities**

### **10.2.1 Principal Investigator**

The principal investigator oversees the management of patient records/case report forms and ensures that a) complete and accurate data will be obtained and provided to the sponsor; b) patient records are maintained to include history, prescribed medication and investigational product(s), measurements, exams, evaluations and adverse events; c) corrections are applied to clinical research data according to principles of good research practice (i.e., single-line delete, date and initial). He or she will ensure that there is correlation between the case report forms and the source documents.

### **10.2.2 Research Coordinator**

A research coordinator creates, collects and organizes clinical trial documentation. He or she ensures that source documentation and data abstraction and entry are being done at protocol specified time points.

### **10.2.3 Research Nurse/Medical Staff**

The research nurse and medical staff documents protocol-required care or assessment of the subject's outcomes, adverse events and compliance to study procedures.

### **10.2.4 Biostatistician**

The biostatistician may assist in CRF development (content and design), dataset specifications (annotation of CRFs and record layout) and validation.

### 10.3 Source Documents

Source documents for clinical information (patient history, diagnosis, clinical and diagnostic test reports, etc.) are maintained in the patient's clinical file.

All source documents will be written following ALCOA standards:

ALCOA Attribute	Definition
Attributable	Clear who has documented the data.
Legible	Readable and signatures identifiable.
Contemporaneous	Documented in the correct time frame along with the flow of events. If a clinical observation cannot be entered when made, chronology should be recorded. Acceptable amount of delay should be defined and justified.
Original	Original, if not original should be exact copy; the first record made by the appropriate person. The investigator should have the original source document.
Accurate	Accurate, consistent and real representation of facts.
Enduring	Long-lasting and durable.
Available and accessible	Easily available for review by treating physicians and during audits/inspections. The documents should be retrievable in reasonable time.
Complete	Complete until that point in time.
Consistent	Demonstrate the required attributes consistently.
Credible	Based on real and reliable facts.
Corroborated	Data should be backed up by evidence.

### 10.4 Case Report Forms

The principal investigator and/or his/her designee will prepare and maintain adequate and accurate participant case histories with observations and data pertinent to the study. Study-specific case report forms (CRFs) will document safety and treatment outcomes for safety monitoring and data analysis. All study data will be entered into OnCore® via standardized CRFs, in accordance with the study calendar, using single data entry with a secure access account. The clinical research coordinator will complete the CRFs as soon as possible upon completion of the study visit; the investigator will review and approve the completed CRFs.

The information collected on CRFs shall be identical to that appearing in original source documents. Source documents will be found in the patient's medical records maintained by MCWCC personnel. All source documentation should be kept in separate research folders for each patient.

In accordance with federal regulations, the investigator is responsible for the accuracy and authenticity of all clinical and laboratory data entered onto CRFs. The principal investigator will

approve all completed CRFs to attest that the information contained on the CRFs is true and accurate.

All source documentation and data will be available for review/monitoring by the MCWCC DSMC and regulatory agencies.

### **10.5 Study Record Retention**

The principal investigator is required to prepare and maintain adequate and accurate case histories that record all observations and other data pertinent to the investigation on everyone administered the investigational intervention or employed as a control in the investigation. Case histories include the case report forms and supporting data including, for example, signed and dated consent forms and medical records including, for example, progress notes of the physician, the individual's hospital chart(s), and the nurses' notes. The case history for each individual shall document that informed consent was obtained prior to participation in the study.

Study documentation includes all CRFs, data correction forms or queries, source documents, sponsor-investigator correspondence, monitoring logs/letters, and regulatory documents (e.g., protocol and amendments, IRB correspondence and approval, signed patient consent forms).

Source documents include all recordings of observations or notations of clinical activities and all reports and records necessary for the evaluation and reconstruction of the clinical research study.

## APPENDIX 1. PERFORMANCE STATUS CRITERIA

ECOG Performance Status Scale		Karnofsky Performance Scale	
Grade	Descriptions	Percent	Description
0	Normal activity Fully active, able to carry on all predisease performance without restriction	100	Normal, no complaints; no evidence of disease
		90	Able to carry on normal activity; minor signs or symptoms of disease
1	Restricted in physically strenuous activity but ambulatory and able to carry out work of a light or sedentary nature (e.g., light housework, office work)	80	Normal activity with effort; some signs or symptoms of disease
		70	Cares for self but unable to carry on normal activity or to do active work
2	Ambulatory and capable of all selfcare, but unable to carry out any work activities; up and about more than 50% of waking hours	60	Requires occasional assistance but is able to care for most of personal needs
		50	Requires considerable assistance and frequent medical care
3	Capable of only limited self-care; confined to bed or chair more than 50% of waking hours.	40	Disabled; requires special care and assistance
		30	Severely disabled; hospitalization indicated although death not imminent
4	Completely disabled; cannot carry on any selfcare; totally confined to bed or chair	20	Very ill; hospitalization indicated Although death not imminent
		10	Moribund
5	Dead	0	Dead

## APPENDIX 2. LOST TO FOLLOW-UP LETTER

Date: \_\_\_\_\_

Dear \_\_\_\_\_,

The research study team has been unable to contact you regarding the clinical trial (A Pilot Study Analyzing Pre-Operative Stereotactic Radiosurgery (SRS) With Gamma Knife® (GK) IconTM for Brain Metastases) in which you participated.

We would like to discuss how you are doing and if we may continue contacting you.

Please contact us at

---

Sincerely,

---

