## **2.4 Secondary Endpoint(s)**

1. CNS progression-free survival and overall survival will be evaluated at six, 12, and 18 months following surgical resection.
2. Rates of leptomeningeal carcinomatosis using preoperative GK-SRS will be documented and compared to historically cited rates for postoperative GK-SRS.
3. Incidence of radiation necrosis will be measured by post-treatment MRI.
4. Quality of life measures will be collected and will be compared to historically cited data.

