### **Consent Withdrawal**

A subject may decide to withdraw from the study at any time. MCWCC CTO will follow its IRB of record's SOPs regarding consent withdrawal.

If a subject intends on withdrawing consent, staff should confirm which of the following options the subject chooses and document the discussion:

- Full consent withdrawal with no study follow-up.
- Selective consent withdrawal from interventional portion of the study but agree to continued follow-up of associated clinical outcome information.

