## **4.7 Lost to Follow-up**

The following actions must be taken if a participant fails to return to the clinic for a required study visit and/or is unable to be reached for follow-up:

- The investigator or designee must make every effort to regain contact and/or reschedule a missed visit with the participant.
- A participant is deemed lost to follow-up if his/her status cannot be obtained after *all* of the following occurs at two consecutive scheduled protocol calendar timepoints:
  - Three telephone calls (at least one day apart) from the study team are unanswered  

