**AND**
  - A letter to the participant's last known mailing address goes unanswered (refer to Appendix 2).  

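### Section 4.7 names no source of vital status before a participant is declared lost, so a death that stays unknown is dropped under 7.3 and raises estimated overall survival

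*Combined protocol and SAP*

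**What the plan says.** Section 2.4 sets the endpoint: "CNS progression-free survival and overall survival will be evaluated at six, 12, and 18 months following surgical resection". Section 3.2 adds that survival will be compared with historical rates.

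Section 4.7 gives the rule for loss. It opens with a duty: "The investigator or designee must make every effort to regain contact and/or reschedule a missed visit with the participant". Then: "A participant is deemed lost to follow-up if his/her status cannot be obtained after" a set of steps, with the qualifier that all "of the following occurs at two consecutive scheduled protocol calendar timepoints". The steps are:

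- "Three telephone calls (at least one day apart) from the study team are unanswered"
- "A letter to the participant's last known mailing address goes unanswered (refer to Appendix 2"
- the attempts are documented.

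Lost status is reversed if the subject later contacts the team. Nothing is said about a death learned of later.

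The Appendix 2 letter addresses the patient: "We would like to discuss how you are doing and if we may continue contacting you". It does not ask a relative or carer to reply.

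The study calendar schedules follow-up every three months to 18 months. It has no survival or vital-status row, and AE reporting is not marked in the follow-up column. Section 6.2.2 ends SAE reporting, which includes death, 30 days after the last dose.

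Section 7.3 excludes the data of patients who do not complete follow-up from the primary and secondary objectives. Section 7.2 names Kaplan-Meier for progression-free survival and gives no censoring rule for overall survival.

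**The concern.** Calls to the participant and a letter to the participant's own address work poorly when the participant has died, and death is the event that overall survival counts. Repeating the same steps about three months later does not change that. The stated effort is directed at regaining contact or rebooking a visit, not at establishing whether the patient is alive, and the protocol does not define what status means.

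Entry requires an estimated median survival of at least six months and follow-up runs to 18 months, so deaths during follow-up are to be expected. If some stay unknown, being lost becomes associated with being dead. Estimated overall survival is then too high, and so is the death component of CNS progression-free survival. The comparison with historical rates would tilt in favor of preoperative radiosurgery. No later analysis can recover deaths that were never looked for.

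**Working it through.** The documents state no survival rate, dropout rate or number of events, so there is no planned figure to reproduce. The check has two parts.

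**Tracing the procedure.** Take a patient who dies three months or more after treatment without the team hearing of it. The next visit is missed, and three calls and a letter go unanswered. The same happens at the following visit, and the attempts are documented. Status has not been obtained, so the rule is met. The calendar prompts no other enquiry, and the SAE window has closed. The patient is entered as lost and section 7.3 removes the data.

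**Size in a small cohort.** Inputs: N = 10, the number of completed subjects planned. Assumed: D true deaths by the landmark, of which m are hidden.

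- True survival = (10 − D)/10.
- Under exclusion (section 7.3), estimated survival = (10 − D)/(10 − m).
- For comparison only, if hidden deaths were censored at their own times, Kaplan-Meier survival is the product of (1 − 1/r) over the detected deaths, with r falling by one at every death, hidden or not. This is averaged over which deaths are hidden. For D = 3 and m = 1 the three cases are 77.8%, 78.75% and 80%, with mean 78.8%.

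| D | True | Excluded, m = 1 | Excluded, m = 2 | Censored, m = 1 | Censored, m = 2 |
|---|---|---|---|---|---|
| 3 | 70% | 7/9 = 77.8% | 7/8 = 87.5% | 78.8% | 88.8% |
| 5 | 50% | 5/9 = 55.6% | 5/8 = 62.5% | 57.5% | 66.0% |
| 7 | 30% | 3/9 = 33.3% | 3/8 = 37.5% | 35.7% | 42.4% |

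Under the plan's own rule, one hidden death adds 7.8, 5.6 or 3.3 points, and two add 17.5, 12.5 or 7.5. If every death is ascertained and counted, the estimate returns to the true value.

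**Size as a share of deaths.** Assume exponential survival with median 12 months, a last visit at 19 months, and a fraction f of deaths up to then hidden and excluded. S(18) = 2^(−18/12) = 0.354 and S(19) = 2^(−19/12) = 0.334. Estimated 18-month survival = [S(18) − f(S(18) − S(19))] / [1 − f(1 − S(19))].

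- f = 0.1: 0.352/0.933 = 38%
- f = 0.2: 0.350/0.867 = 40%
- f = 0.3: 0.348/0.800 = 43%

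The true value is 35%. With f = 0.2 and a median of 9 months, 25% becomes 0.246/0.846 = 29%. With a median of 18 months, 50% becomes 0.496/0.896 = 55%. The medians and f are all assumptions.

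**The case against.** The strongest reply is that section 4.7 is more careful than a list of unanswered calls. Status must be unobtainable, the attempts must fail on two scheduled visits in a row, and the team has a general duty of effort. A patient whose death is known by any route does not meet the rule. A relative may pick up the telephone or answer the letter. This is a single center working from its own medical records, so many deaths would come to light anyway. Overall survival is secondary and descriptive in a feasibility pilot, and sampling error dwarfs the bias: the exact 95% interval for 4 of 10 is about 12% to 74%.

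Most of this stands as a limit on the claim. A reader might infer that vital status is never checked, or that any patient who dies will be recorded as lost. The status condition rules out both readings, and the bias arises only for deaths that remain unknown. A reader might also contrast section 4.6, which offers "Selective consent withdrawal from interventional portion of the study but agree to continued follow-up of associated clinical outcome information", and conclude that the plan accepts outcome follow-up without contact for those patients. The text does not say without contact, so no such asymmetry is shown.

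What the reply does not supply is a required source. Status is undefined, the stated effort is to regain contact, and whether the chart or family is consulted is left to habit. Wide intervals do not excuse an error that always runs in one direction.

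**Conclusion.** The point holds in a conditional form. The listed steps reach only the participant, no vital-status source is named, and neither the calendar nor the SAE window provides a backstop. A death not otherwise learned of is recorded as loss and excluded, and this can only raise estimated survival. One hidden death among 10 adds about 3 to 8 points under section 7.3. The documents give no basis for how often this would happen, so the figures show sensitivity and do not predict.

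The larger censored figures in the table do not describe the stated analysis, because 7.3 excludes these patients. They do show that replacing exclusion with censoring would not cure the problem while deaths stay hidden.

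A reader might go further and infer that 7.3 also discards patients known to have died before 18 months. The documents do not say whether death counts as failing to complete follow-up, so this is an ambiguity to close and not an established exclusion. It does mean that a vital-status check in 4.7 helps only if 7.3 lets the death count. For a secondary endpoint in a pilot this is a worthwhile, inexpensive improvement and not a threat to the primary feasibility objective.

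**What to change.** In section 4.7:

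- Define status as including vital status.
- Before loss is entered in OnCore, require a documented check of the medical record, the treating oncologist or listed next of kin, and public death records.
- Repeat the check for every lost patient at the data cut.
- Enter any death found, with its date, as an overall-survival event.

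In Appendix 2, add a line inviting a family member to reply if the patient cannot.

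In section 7.3, state that deaths found count in overall survival, and that patients whose status remains unknown are censored at the date last known alive and not removed.

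The cost is a few sentences and some coordinator time for at most 15 patients at one center. The consent and HIPAA wording may need to mention the record search and the contact with family.
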